9.1.5. Unsolicited Adverse Event

Unsolicited AEs are defined as any AEs reported spontaneously by the participant, observed by the study staff during study visits or those identified during review of medical records or source documents. Solicited AEs with an onset after the 7-day solicitation period (Day 1-7) will be considered unsolicited AEs. An unsolicited AE is defined as any AE that is volunteered from the participant and occurs within 28 days after vaccination (Day 1-28).

The percentage of participants with unsolicited AEs onset date within day 1-28 will be provided by age group, dose group, by grade, outcome and causality (any, fatal, causally related, fatal/causally related).

The number and percentage of participants with unsolicited AEs onset date within day 1-28 will be provided by SOC and PT for each dose group (any grade, grade 3, related).

Unsolicited AEs will be summarized and listed up to day 28 after study vaccination (Day 1-28).

A data listing for all Unsolicited AEs will be provided by age group, dose group and participant number.

9.1.6. Adverse Events of Special Interest

An AESI (serious or nonserious) is defined as an AE or SAE of scientific and medical concern specific to the sponsor's product or program, for which ongoing monitoring and rapid communication by the investigator to the sponsor could be appropriate (ICH E2F; CIOMS VI). Adverse events of special interest will include the following events:

- Virologically-confirmed SARS-CoV-2 infections (see protocol Section 6.6 for disease definitions)
- Potential immune-mediated disorders (see protocol Section 13.4 for definitions)
- Anaphylaxis or severe hypersensitivity within 24 hours after study vaccine administration
- Pericarditis or myocarditis

AESIs will be identified using MedDRA queries and Investigator identification as per eCRF. Refer to appendix 15.3 for details on these queries.

The percentage of participants with AESIs with onset date within day 1-28 and within day 1-180, identified by either the investigator or by MedDRA queries will be provided by SOC and PT for each dose group.

Similarly, AESIs that are related to COVID-19 will be presented in a separate listing by age group, dose group and participant number.

AESIs will be reported until exit from study (up to day 180 after the study vaccine administration, Day 1-180).

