1.2 Risk/Benefit Considerations

Detailed information about the known and expected risks and benefits and reasonably expected AEs of the CV2CoV vaccine is provided in the IB. A high-level summary is provided here.

Participants are not expected to directly benefit from study participation. However, their participation in this study will contribute to generating information regarding the vaccine platform being evaluated and the potential for this construct to be further evaluated in Phase 2 and 3 clinical trials.

Due to the lack of experience in human participants, there is currently not enough information available about the relationship of AEs and the administration of the CV2CoV mRNA investigational vaccine.

As for any vaccine, local (eg, pain, swelling, erythema at the injection site) and systemic (eg, fatigue, headache, myalgia) postvaccination symptoms may occur within the first 3 days of vaccination, and are anticipated to resolve within a few days of onset.

Important potential risks for the CV2CoV mRNA investigational vaccine are the following:

- Hypersensitivity reactions, including anaphylaxis.
- Myocarditis.
- Pericarditis.
- Syncope and vasovagal reactions to injection.
- Vaccine-associated disease enhancement is an important risk for all SARS-CoV-2 vaccines.

To mitigate these important potential risks, the following risk strategies have been implemented in the study:

- All participants will remain under observation at the vaccination center for at least 60 minutes after vaccination.
- Participants with history of hypersensitivity or severe allergic reaction to any
 previous vaccine or any component of the IP are excluded from the study enrollment
 and participants will be instructed to contact the study site immediately for
 occurrence of any possible hypersensitivity reaction within 1 day of vaccination.
- Participants at increased risk of myocarditis or pericarditis and participants with history of myocarditis or pericarditis are excluded from the study enrolment.
- Participants will be instructed (via the informed consent form) to be alert to symptoms of myocarditis or pericarditis and to contact the study site immediately if occurrence of any of these symptoms.
- As syncope and other anxiety-related reactions may occur before vaccination, the
 decision to vaccinate the participant will be depending on the clinical judgment of the
 investigator.

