6.1.1.1.4 Adverse Events of Special Interest

An AESI (serious or nonserious) is defined as an AE or SAE of scientific and medical concern specific to the sponsor's product or program, for which ongoing monitoring and rapid communication by the investigator to the sponsor could be appropriate (ICH E2F; CIOMS VI).

For this study, AESIs will include the following events:

- Virologically confirmed SARS-CoV-2 infections (see Section 6.6 for disease definitions)
- Potential immune-mediated disorders (Appendix 13.4)
- Anaphylaxis or severe hypersensitivity within 24 hours after study vaccine administration
- Pericarditis or myocarditis

Refer to Section 6.1.1.3.1 for reporting AESIs.

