13.4 Appendix 4: Potential Immune-mediated Diseases

Potential immune-mediated diseases are a subset of AEs that include autoimmune diseases and other inflammatory and/or neurologic disorders of interest which may or may not have an autoimmune etiology. Adverse events that need to be recorded and reported as pIMDs include those listed in Table 13-3.

However, the investigator will exercise their medical and scientific judgment in deciding whether other diseases have an autoimmune origin (that is pathophysiologically involving systemic or organ-specific pathogenic autoantibodies) and should also be recorded as a pIMD.

When there is enough evidence to make any of the diagnoses mentioned in Table 13-3, the AE must be reported as a pIMD. Symptoms, signs, or conditions which might (or might not) represent the above diagnoses, should be recorded and reported as AEs but not as pIMDs until the final or definitive diagnosis has been determined, and alternative diagnoses have been eliminated or shown to be less likely.

In order to facilitate the documentation of pIMDs in the eCRF, a pIMD standard questionnaire will be available to investigators.

Once a pIMD is diagnosed (serious or nonserious) in a study participant, the investigator (or designate) must complete, date, and sign an electronic Expedited Adverse Events Report.

Table 13-3 List of Potential Immune-Mediated Diseases

Medical Concept	Additional Notes
Blood disorders and coagulopathies	
Antiphospholipid syndrome	
Autoimmune aplastic anemia	
Autoimmune hemolytic anemia	Includes warm antibody hemolytic anemia and cold antibody hemolytic anemia
Autoimmune lymphoproliferative syndrome (ALPS)	
Autoimmune neutropenia	
Autoimmune pancytopenia	
Autoimmune thrombocytopenia	Frequently used related terms include: "autoimmune thrombocytopenic purpura", "idiopathic thrombocytopenic purpura

`	,
	(ITP)", "idiopathic immune thrombocytopenia", "primary immune thrombocytopenia".
Evans syndrome	
Pernicious anemia	
Thrombosis with thrombocytopenia syndrome (TTS)	
Thrombotic thrombocytopenic purpura	Also known as "Moschcowitz-syndrome" or "microangiopathic hemolytic anemia"
Cardio-pulmonary inflammatory disorders	
Idiopathic Myocarditis/Pericarditis	Including but not limited to:
	Autoimmune / Immune-mediated myocarditis
	Autoimmune / Immune-mediated pericarditis
	Giant cell myocarditis
Idiopathic pulmonary fibrosis	Including but not limited to:

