	Erythema induratum (also known as nodular vasculitis)			
	Henoch-Schonlein purpura (also known as IgA vasculitis)			
	Microscopic polyangiitis			
	Necrotizing vasculitis			
	Polyarteritis nodosa			
	Single organ cutaneous vasculitis, including leukocytoclastic vasculitis, hypersensitivity vasculitis and acute hemorrhagic edema of infancy (AHEI)			
	Wegener's granulomatosis			
Other (including multisystemic)				
Anti-synthetase syndrome				
Capillary leak syndrome	Frequently used related terms include: "systemic capillary leak syndrome (SCLS)" or "Clarkson's Syndrome"			
Goodpasture syndrome	Frequently used related terms include: "pulmonary renal syndrome" and "anti-Glomerular Basement Membrane disease (anti-GBM disease)"			
Immune-mediated enhancement of disease	• Includes vaccine-associated enhanced disease (VAED and VAERD). Frequently used related terms include "vaccine-mediated enhanced disease (VMED)", "enhanced respiratory disease (ERD)", "vaccine-associated enhancement of infection", "disease enhancement", "immune enhancement", and "antibody-dependent enhancement (ADE)"			
Immunoglobulin G4 related disease				
Langerhans' cell histiocytosis				
Multisystem inflammatory	Including but not limited to:			
syndromes	Kawasaki's disease			
	Multisystem inflammatory syndrome in adults (MIS-A)			
	Multisystem inflammatory syndrome in children (MIS-C)			
Overlap syndrome				
Raynaud's phenomenon				
Sarcoidosis	Includes Loefgren syndrome			

Protocol 217741 (CV2 SARS-COV2-002 BST) Amendment 2

Susac's syndrome

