15.3. MedDRA queries for identifying AESIs

The tables below are MedDRA version specific and may be revised with a new MedDRA version:

Table 15.3 1: Preferred terms for AESIs which are not pl	MDs
--	-----

	Autoimmune myocarditis
	Eosinophilic myocarditis
Mucoorditio	Giant cell myocarditis;
Myocarditis	Hypersensitivity myocarditis
	Immune-mediated myocarditis
	Myocarditis
	Autoimmune pericarditis
	Pericarditis
Pericarditis	Pericarditis adhesive
	Pericarditis constrictive
	Pleuropericarditis
Severe Hypersensitivity	Grade 3 unsolicited AEs under MedDRA SMQ hypersensitivity, narrow search
	(includes anaphylaxis), with an onset within 24 hours after vaccination

COVID 19 infection will be based on PCR test (there is no MEDRA query)

Event Category	Immune-Mediated Disorder	MedDRA PT	PT Code
Neuroinflammatory	Cranial nerve disorders and	Anosmia	10002653
disorders	inflammations	IIIrd nerve paralysis	10021283
		IIIrd nerve paresis	10054202
		IVth nerve paralysis	10023110
		IVth nerve paresis	10054201
		Trigeminal palsy	10049788
		Trigeminal nerve paresis	10068008
		VIth nerve paralysis	10047641
		VIth nerve paresis	10071044
		Facial paralysis	10016062
		Facial paresis	10051267
		Acoustic neuritis	10063162
		Glossopharyngeal nerve paralysis	10051270
		Tongue paralysis	10031270
		Vagus nerve paralysis	10043572
		Vocal cord paralysis	10004001
		Vocal cord paresis	10047074
		XIth nerve paralysis	10049234
		Hypoglossal nerve paralysis	10048842
		Hypoglossal nerve paresis	10067129
		Bulbar palsy	10006542
		Oculofacial paralysis	10030069
		Neuritis cranial	10029244
		Cranial nerve disorder	10061093
		Paresis cranial nerve	10061911
		Cranial nerve paralysis	10061908
		Cranial nerve palsies multiple	10011314
		Optic neuritis	10030942
	Multiple sclerosis	Multiple sclerosis	10028245
		Radiologically isolated syndrome	10079292
		Primary progressive multiple sclerosis	10063401
		Progressive multiple sclerosis	10053395
		Marburg's variant multiple sclerosis	10067067
		Secondary progressive multiple sclerosis	10063400
		Multiple sclerosis relapse	10048393
		Relapsing multiple sclerosis	10080700
		Multiple sclerosis relapse prophylaxis	10070495
		Progressive relapsing multiple sclerosis	10067063
		Relapsing-remitting multiple sclerosis	10063399
		Tumefactive multiple sclerosis	10078556
		Expanded disability status scale score decreased	10071385
		Expanded disability status scale score decreased	10071384
	Myelitis / Transverse myelitis	Myelitis transverse	10071564

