	ingentis / fransverse myentis	Myelitis	10028524
		Acute flaccid myelitis	10028524
		Noninfectious myelitis	10082097
	Guillain-Barré syndrome	Guillain-Barré syndrome	100/1/64
	Sumani-Barre Synuronne		
	A outo diagonain-t-1	Miller Fisher syndrome	10049567
	Acute disseminated	Demyelination	10012305
	encephalomyelitis and	Intramyelinic oedema	10083038
	demyelination (including site	Autoimmune demyelinating disease	10075688
	specific variants)	Clinically isolated syndrome	10071068
		Leukoencephalomyelitis	10048999
		Leukoencephalopathy	10024382
		Acute disseminated encephalomyelitis	10000709
		Acute haemorrhagic leukoencephalitis	10058994

Table 15.3 2: Preferred terms for AESIs which are pIMDs

			10010050
		Concentric sclerosis	10010252
		Encephalitis periaxialis diffusa	10049020
		Limbic encephalitis	10078012
		Neuromyelitis optica spectrum disorder	10077875
		Neuromyelitis optica pseudo relapse	10080353
		Autoimmune encephalopathy	10075691
		Bickerstaff's encephalitis	10076985
		Noninfective encephalitis	10074712
		Encephalitis autoimmune	10072378
		Immune-mediated encephalitis	10083074
		Rasmussen encephalitis	10071141
		Encephalitis allergic	10056387
		Encephalitis brain stem	10048997
		Encephalitis haemorrhagic	10014589
		Encephalomyelitis	10014619
		Noninfective encephalomyelitis	10074713
		Encephalitis post immunisation	10014602
		Panencephalitis	10056332
		Encephalitis toxic	10014607
		Chronic lymphocytic inflammation with pontine perivascular	10075197
		enhancement responsive to steroids	10010171
	Myasthenia gravis	Myasthenia gravis	10028417
	1.1 uotienta Bravio	Myasthenia gravis crisis	10023417
		Ocular myasthenia	10049168
		Myasthenic Syndrome	10049100
	Autoimmune / Immune-	Autoimmune neuropathy	1002042
	mediated peripheral	Immune-mediated neuropathy	10070439
	neuropathies and plexopathies	Neuritis	
	neuropatities and prexopatities		10029240
		Anti-myelin-associated glycoprotein associated	10078324
		polyneuropathy	1000170
		Subacute inflammatory demyelinating polyneuropathy	10081726
		Chronic inflammatory demyelinating polyradiculoneuropathy	10057645
		Lewis-Sumner syndrome	10065580
		Demyelinating polyneuropathy	10061811
		Polyneuropathy idiopathic progressive	10036111
		Multifocal motor neuropathy	10065579
		Acute motor-sensory axonal neuropathy	10076657
		Acute motor axonal neuropathy	10076658
		Cervical neuritis	10008293
		Mononeuritis	10027910
		Mononeuropathy multiplex	10027918
		Brachial plexopathy	10065417
		Radiculitis brachial	10037778

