	Antiphospholipid syndrome	10002817
	Pernicious anaemia	10034695
Autoimmune / immune-	Glomerulonephritis rapidly progressive	10018378
mediated glomerulonephritis	IgA nephropathy	10021263
	IgM nephropathy	10077209
	C1q nephropathy	10081461
	Glomerulonephritis membranous	10018372
	Glomerulonephritis membranoproliferative	10018370
	Membranous-like glomerulopathy with masked IgG-kappa	10083098
	deposits	100((452
	Mesangioproliferative glomerulonephritis	10066453
	Anti-glomerular basement membrane disease	10081981
	Autoimmune nephritis	10077087
	Immune-mediated nephritis	10083070
	Chronic autoimmune glomerulonephritis	10073016
	Tubulointerstitial nephritis and uveitis syndrome	10069034
Ocular autoimmune / immune-	Uveitis	10046851
mediated diseases	Vogt-Koyanagi-Harada disease	10082001
	Ocular pemphigoid	10067776
	Autoimmune retinopathy	10071578
	Acute macular outer retinopathy	10079367
	Autoimmune uveitis	10075690
	Immune-mediated uveitis	10083069
	Autoimmune eye disorder	10081123
Autoimmune / immune-	Autoimmune myocarditis	10064539
mediated heart disease	Immune-mediated myocarditis	10082606
	Autoimmune pericarditis	10079058
Sarcoidosis	Sarcoidosis	10039486
	Pulmonary sarcoidosis	10037430
	Neurosarcoidosis	10037430
	Cutaneous sarcoidosis	10078011
	Liver sarcoidosis	10068664
	Muscular sarcoidosis	
		10028365
0'" 1	Ocular sarcoidosis	10065700
Sjögren's syndrome	Sjogren's syndrome	10040767
Autoimmune lung disease	Idiopathic pulmonary fibrosis	10021240
	Idiopathic interstitial pneumonia	10078268
	Interstitial lung disease	10022611
	Pulmonary fibrosis	10037383
	Autoimmune lung disease	10080701
	Immune-mediated pneumonitis	10082452
Goodpasture's syndrome	Goodpasture's syndrome	10018620
Raynaud's phenomenon	Raynaud's phenomenon	10037912

Note: This list is reviewed for each new MedDRA version and the list applicable at database lock will be documented within the ADAM package.

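### The SAP's query lists for adverse events of special interest do not implement the protocol definition they serve: listed diagnoses have no term, anosmia is added, and anaphylaxis is queried only at Grade 3

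*SAP*

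**What the plan says.** Protocol 6.1.1.1.4 defines four kinds of AESI: virologically confirmed SARS-CoV-2 infection, the potential immune-mediated disorders of Appendix 13.4, "Anaphylaxis or severe hypersensitivity within 24 hours after study vaccine administration", and myocarditis or pericarditis. Protocol 13.4 requires diagnoses in Table 13-3 to be reported as pIMDs. It also says that signs and symptoms which may or may not represent such a diagnosis stay ordinary adverse events until the diagnosis is definitive.

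SAP 9.1.6 repeats the four kinds, refers to protocol 13.4 for the pIMD definition, and adds the operating rule: "AESIs will be identified using MedDRA queries and Investigator identification as per eCRF". The summaries count an event found by either route, by system organ class and preferred term within dose group.

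The queries are in SAP 15.3. One table holds the non-pIMD terms, where the hypersensitivity row reads "Grade 3 unsolicited AEs under MedDRA SMQ hypersensitivity, narrow search" and notes that anaphylaxis falls inside it. The other is headed "Table 15.3 2: Preferred terms for AESIs which are pIMDs". A closing note says "This list is reviewed for each new MedDRA version" and that the list in force at database lock will be documented. SAP Section 13 records no change to the planned analysis.

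**The concern.** The percentage of participants with AESIs through Day 180 is part of the primary endpoint in both documents. The query is there to pick up events that the investigator did not flag, so its value depends on its covering the definition.

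The SAP list is narrower than the protocol list in some places and wider in others, and the SAP does not declare the difference. One uncovered entry, "Immune-mediated enhancement of disease", concerns a risk that protocol 1.2 singles out: "Vaccine-associated disease enhancement is an important risk for all SARS-CoV-2 vaccines". In the other direction, loss of smell is one of the COVID-19 symptoms in protocol 6.6, yet the SAP list treats anosmia as a pIMD term in its own right. The note on list review is tied to dictionary versions, and nothing in it provides for checking the list against Table 13-3.

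**Working it through.** The documents give no AESI rate or count, so there is no figure to reproduce. The check is a comparison of the lists, followed by the counting rule.

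**1. The lists side by side** (protocol 6.1.1.1.4 and Table 13-3; SAP 9.1.6 and 15.3)

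| Protocol | SAP 15.3 |
|---|---|
| Thrombosis with thrombocytopenia syndrome | no term |
| Capillary leak syndrome | no term (capillaritis is a different entry) |
| Immune-mediated disease enhancement | no term |
| IgG4-related disease | no term |
| Susac's syndrome | no term |
| Pyoderma gangrenosum | no term |
| Autoimmune lymphoproliferative syndrome | no term |
| Pulmonary alveolar proteinosis | no term |
| Multisystem inflammatory syndromes: Kawasaki's disease, MIS-A, MIS-C | Kawasaki's disease only |
| Cranial nerve row: open-ended, anosmia not named | anosmia listed |
| Anaphylaxis (no grade stated) or severe hypersensitivity, within 24 hours | one query, Grade 3, within 24 hours |

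The first eight rows are concepts with no readable term of their own. Four more appear to be in the same position: insulin autoimmune syndrome, autoimmune hyperlipidemia, autoimmune disease of the testis and ovary, and reactive granulomatous dermatitis. Broad SAP terms, such as autoimmune lung disease or autoimmune endocrine disorder, might catch some of these, depending on coding. Part of the thrombocytopenic purpura block is garbled in the text available, but no readable row contains the missing concepts.

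**2. What a missing term does.** A participant counts if the investigator or the query identifies an event. If no query term exists, the event is lost with probability 1 − q, where q is the probability that the investigator flags it. The documents do not give q. For an assumed q of 0.8 to 1.0, the loss is 20% to 0% of such events.

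**3. What anosmia does.** The endpoint counts participants.
- With confirmed SARS-CoV-2 infection, the participant is already an AESI case. Anosmia adds 0 to the percentage and one preferred-term row to the table.
- Without confirmed infection and without another AESI, the participant is added.

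**4. Weight of one participant.** The planned dose group is 30, so 1/30 = 3.3 percentage points. For scale, exact 95% intervals:
- 0/30: upper limit 1 − 0.025^(1/30) = 11.6%, so 0% to 11.6%.
- 1/30: 0.1% to 17.2%.

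**5. How often anosmia could matter.** The documents give no rate r of anosmia without confirmed infection. The probability of at least one case in a group is 1 − (1 − r)^30. The same formula reproduces the plan's own figures for any adverse event: 1 − 0.95^30 = 78.5% and 1 − 0.90^30 = 95.8%. For assumed values of r:

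| Assumed r | P(at least one in 30) |
|---|---|
| 0.5% | 14% |
| 1% | 26% |
| 2% | 45% |
| 5% | 79% |

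**6. Anaphylaxis.** Protocol 6.1.1.2.1 grades events by their interference with everyday activities. An anaphylaxis recorded as Grade 1 or 2 would meet the plain reading of the definition but fall outside the query. It would then be counted only if the investigator flagged it.

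**The case against.** The strongest reply is that the SAP plans no count based on the query alone. Investigators must report Table 13-3 diagnoses as pIMDs, and AESIs go to pharmacovigilance within 24 hours of the site learning of them, so the main route covers the full definition. Events that are serious or medically attended also appear in their own primary-endpoint tables and listings through Day 180. All of this stands, and it limits the loss. It does not make the list right, because the query is the only independent check on the investigator and is absent for these concepts.

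On disease enhancement, a reader might infer that such cases would vanish from the AESI count. The documents do not support that. A case with confirmed infection is already an AESI, and SAP 8.4 separately tabulates severe infection and hospitalization or death due to infection. What the query can fail to supply is the pIMD label.

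On anosmia, a reader might infer that loss of smell from COVID-19 inflates the percentage, or is tabulated as a neuroinflammatory disorder. Neither follows. The infected participant already counts, and the planned AESI tables use system organ class and preferred term, not the category column of the term list. The cranial nerve row is also open-ended, so anosmia is unnamed but not excluded. What stands is the conflict with the protocol's own rule on symptoms without a definitive diagnosis.

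On anaphylaxis, the word severe could be read as governing both terms, and Grade 3 is the top grade on the general adverse event scale. On-site observation (at least 60 minutes, about 4 hours for sentinels) also makes an unflagged case less likely. The plain reading still sets no grade for anaphylaxis, and the ambiguity should be settled in the SAP.

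Finally, the list at database lock governs, so it can still be revised. That gives the sponsor a route to the correction, but no passage commits to making it.

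**Conclusion.** The mismatch holds on a direct reading: at least 8 Table 13-3 concepts without a query term, MIS-A and MIS-C absent, anosmia added, and anaphylaxis restricted to Grade 3. The list therefore contradicts the definition that SAP 9.1.6 says it applies, and it feeds a primary endpoint.

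The consequence is conditional. The list can miss an event only when the investigator also does not flag it. It can add a participant through anosmia only when there is no confirmed infection and no other AESI. Each such participant is 3.3 points in a group of 30, and more if a group closed below 30.

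A reader might go further and say that the AESI count is wrong in both directions, or that any error is set against an expected count near zero. The documents support neither. The reported count is the union of two routes, and AESIs include every confirmed SARS-CoV-2 infection over about 180 days, for which no rate is given.

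The conclusion rests on the readable text of the tables, on the plain reading of the anaphylaxis definition, and on taking confirmed infection as PCR-confirmed, which is the basis stated in SAP 15.3. The study is descriptive, with no hypothesis test at risk. The point should be corrected before lock.

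**What to change.** Before database lock:

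1. Map each Table 13-3 concept to the preferred terms available in the MedDRA version used, and add the missing ones to SAP Table 15.3-2. Where the dictionary has no suitable term, say so and rely explicitly on investigator identification.
2. Remove anosmia, or count it as a pIMD only after medical review and with no concurrent confirmed infection.
3. Split the hypersensitivity query: anaphylaxis without a grade filter, other hypersensitivity at Grade 3, each with onset within 24 hours.
4. Show investigator-identified and query-only AESIs separately as well as combined, so that the contribution of the list is visible.
5. Extend the list-review note to cover agreement with protocol 6.1.1.1.4 and Table 13-3.

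This is a revision of a term list plus one more split in the AESI table. The downside is a few more cases for medical review.
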